1.0 OBJECTIVES

The overall objective is to determine whether the natural flaxseed lignan, secoisolariciresinol diglycoside (SDG), in amounts providing plasma lignan levels associated with reduced breast cancer risk, will favorably modulate risk biomarkers for breast cancer development. This will provide biologic evidence of SDG's potential for breast cancer chemoprevention. Based on a positive pilot study in which both Ki-67 and the proportion of women with atypical cytomorphology was reduced with 12 months of SDG 50 mg/day, a randomized, placebo-controlled clinical chemoprevention trial will be conducted wherein pre-menopausal women at increased risk for the development of breast cancer will receive Brevail® (200 mg, equivalent to 50 mg of SDG) or matched, blinded placebo for 12 months. A total of 242 subjects will be accrued, randomized 2:1 to SDG vs placebo, with the goal of achieving 220 subjects completing study and evaluable for biomarker change.

The primary objective is to determine if women randomized to 12 months of SDG exhibit greater change in the proportion of breast epithelial cells expressing the proliferation marker Ki-67/MIB-1 in hyperplastic benign breast tissue than do women randomized to placebo.

Secondary objectives are:

- 1) to determine if 12 months of SDG is associated with favorable modulation of other risk biomarkers including cytologic atypia, and serum levels of bioavailable estradiol and testosterone, IGF-I:IGFBP-3 ratio, c-peptide, adiponectin, and leptin.
- 2) to determine if Ki-67 and modulation of other risk biomarkers is correlated with change in blood or urine lignans.
- 3) to determine impact or potential impact on quality of life as measured by the BPQ breast pain questionnaire (a modified McGill Pain questionnaire), The Breast Cancer Prevention Trial (BCPT) Symptom Checklist a menstrual diary for cyclicity and cycle length for women not on cycle modulating contraceptives; and antimullerian hormone (AMH), a measure of follicular reserve.

An exploratory objective is to interrogate SDG's mechanism of action through measurement of changes in hormones, growth factors, gene expression, adipokines and cytokines and proteomic signatures.

The overriding hypothesis is that biomarkers assessed both in serum and in hyperplastic breast tissue obtained by RPFNA from high risk pre-menopausal women will be favorably modulated by 12 months of SDG without negatively affecting quality of life.

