Specifically, it is hypothesized that SDG administration will be associated with

- a reduction in proliferation as measured by Ki-67;
- a reduction in proportion of specimens with cytologic evidence of atypia;
- a favorable tolerability and quality of life profile;
- no significant impact on menstrual cycle length;
- no significant effect on follicular reserves as measured by early follicular phase anti-mullerian hormone in women entering the study between ages 21-35;
- a reduction in breast pain in those women entering the study with mastalgia.

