2.4.4.5 Adverse events

The main expected AEs from SDG were diarrhea, flatulence, and irregular menses. GI symptoms, usually grade 1, were encountered in 42%, irregular menses in 26%, and hot flashes in 6% of subjects. Only two grade 3 AEs were reported. One subject was diagnosed with DCIS on the basis of the mammogram performed prior to the 12 month RPFNA. This was not considered related to the study agent. One subject discontinued study after 3 months because of grade 3 pelvic pain that was thought to be possibly related to study agent

Frequency of adverse events by worst reported per subject.

Number	CTC Grade					
	0	1	2	3	4 or 5	Total
Total	7 (14%)	17 (35%)	23 (47%)	2 (4%)	0 (0%)	49

Change in plasma lignans did not correlate with change in Ki-67, adverse events (AEs), or compliance [101].

[figure not shown]

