6.3.7 Menstrual diary

Women will continue to record days of menstrual bleeding or spotting throughout the trial.

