Evaluation of agent-induced hormonal changes - We will examine whether SDG has any effects on serum levels of bioavailable estradiol, and testosterone, determined at baseline and after 12 months of study medication. We will determine whether addition of SDG alters the frequency or length of menstrual cycles. Effects on follicular reserve will be evaluated with anti-mullerian hormone in a sub-cohort of pre-menopausal women between ages 21 and 35 at study entry. Antimullerian hormone (AMH) is one of the earliest and most sensitive measures of follicular reserve declines for approximately 10 years before the cessation of menses. A distinct advantage for trial purposes is that it does not vary with day of menstrual cycle [119].

Adverse Events and Quality of Life – Change from baseline to 12 months will be assessed for mastalgia (expected in 30-50% of subjects at baseline), menstrual cycle and follicular reserve, and quality of life, as a function of SDG intake, plasma lignan levels and urinary lignan excretion. We will use the breast pain questionnaire (BPQ), which is a modified short form of the McGill Pain questionnaire (SF-MPQ) to assess breast discomfort and the Breast Cancer Prevention Trials (BCPT) Symptom Checklist to monitor quality of life

Correlative analyses will be performed with plasma and urine ENL and total lignans as the independent variable, with modifying variables of baseline BMI age and specific SNPs such as CYP17.

Since this is a phase IIB trial, the power and sample size for the primary endpoint was determined with a two-sided type I error rate of 5%. All subsequent secondary, tertiary and exploratory analyses will also be tested with a two-sided type I error rate of 5%. This may result in an elevated false positive rate for these secondary and tertiary analyses, however, since this is a Phase IIB study, we felt to control the type I error rate for the secondary, tertiary and exploratory analyses would be too conservative.

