7.2 Measurement of Urine Lignans

Spot and overnight (12 hour) collections of urine will be shipped to Fred Hutchinson Cancer Research Center for measurement by [name] using isotope dilution gas chromatography-mass spectrometry in SIM mode [41,112,113], with normalization by creatinine level.

8. Questionnaires

8.1 The BCPT symptom checklist is a 42 item list of problems common to peri and postmenopausal women and those undergoing anti-hormonal treatment in prevention trials. Women are asked if they have had the symptom in the past four weeks. If they answer yes, they are asked to grade the severity (0-4). This tool can be used to compute a total score or individual or related items of interest (e.g., three items relate to joint stiffness and arthralgias) may be scored [117,118].

8.2 The Breast Pain Questionnaire (BPQ), a modified short form of the McGill Pain questionnaire (SF-MPQ), will be used to assess breast discomfort and a possible effect of SDG to ameliorate symptoms of mastalgia [116].

8.3 Changes in menstrual cycle length will be assessed by having subjects complete a menstrual diary for each month they are on study.

8.4 Lignan intake will be assessed at study entry using a questionnaire modified after that developed by Thompson et al. [16,42] which queries intakes and amounts of ~125 foods containing significant amounts of SECO, pinoresinol, matairesinol, and sesamin, all of which can be converted to the mammalian lignans ENL and EDL [16].

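### Irregular menses, a main expected adverse event of SDG, has no planned between-arm analysis aimed at it, and the cycle frequency or length analysis could miss erratic cycling

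*Combined protocol and SAP*

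**What the plan says.** Section 2.4.4.5 reports the pilot: "The main expected AEs from SDG were diarrhea, flatulence, and irregular menses", with "irregular menses in 26%, and hot flashes in 6% of subjects".

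Secondary objective 3 (section 1.0) lists "a menstrual diary for cyclicity and cycle length for women not on cycle modulating contraceptives". The matching hypothesis in section 1.0 is narrower: "no significant impact on menstrual cycle length".

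On data, section 6.3.7 says "Women will continue to record days of menstrual bleeding or spotting throughout the trial", and section 6.5.5 collects the diaries at the end.

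On analysis there are three statements:
- Section 11.2, hormonal changes: "We will determine whether addition of SDG alters the frequency or length of menstrual cycles".
- Section 11.2, adverse events and quality of life: change from baseline to 12 months in "menstrual cycle and follicular reserve, and quality of life, as a function of SDG intake, plasma lignan levels and urinary lignan excretion". Menstrual cycle is not defined there.
- Appendix 1, item 8.3: "Changes in menstrual cycle length will be assessed by having subjects complete a menstrual diary for each month they are on study".

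Adverse events are graded by CTCAE 4.0 (section 8.2.3). Section 11.2 introduces its toxicity comparison as covering moderate or worse events, then defines the critical events as grade 3 toxicity or premature discontinuation, compared by Fisher's exact test. The severity table in section 8.2.3, which serves events without a CTCAE term, labels grade 2 as moderate.

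**The concern.** The objective covers two properties of the cycle, regularity and length. By the time the plan reaches the hypothesis, section 11.2 and Appendix 1, regularity has dropped out. Irregularity is largely variation from cycle to cycle within a woman, plus unscheduled bleeding, and an average length or a yearly count need not respond to either.

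The adverse-event route does not close the gap. The pilot had two grade 3 events, described as DCIS and pelvic pain, and none at grade 4 or 5, so its irregular menses was grade 2 or lower. Section 5.9 says that grade 2 menstrual irregularities do not lead to suspension of the agent, so the harm is also unlikely to surface often as discontinuation.

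Section 3.2 puts forward a low likelihood of gynecologic problems as a reason to expect high uptake. A null finding on cycle length could be cited in support of that while regularity had not been examined. The pilot's 26% has no control rate, and this placebo-controlled trial is where one could be obtained.

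**Working it through.** **The plan's own figure.** No power or sample size is given for any menstrual outcome. The only stated figure is 83% for Ki-67. It reproduces: SE = 6 × √(1/147 + 1/73) = 0.859; 2.5/0.859 = 2.91; Φ(2.91 − 1.96) = 0.83. It does not bear on this point.

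**Inputs from the documents.**
- 148 evaluable women not on oral contraceptives (section 11.1), at 2:1 about 99 on SDG and 49 on placebo.
- 242 randomised, about 161 and 81.
- 26% affected on SDG, taken from the pilot.
- Two-sided 5% level.

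**Inputs assumed, because the documents give none.** Placebo rate; mean cycle length; between- and within-woman SDs; the form that irregularity takes.

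**Case 1: short and long cycles cancel.** An affected woman has cycle lengths with the same mean μ and a larger SD. The expected arm difference in mean length is (0.26 − placebo rate) × 0 = 0, so a test on the mean rejects at about its false-positive rate whatever the sample size. Simulation: 3,000 trials per scenario; μ ~ N(29, 3) days; 2 baseline and 12 on-study cycles; within-woman SD 3 days, rising to 6 or 8 if affected.

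| Affected, SDG vs placebo | t-test, change in mean length | Welch test, log within-woman SD |
|---|---|---|
| 26% vs 5% | 4.1% / 3.9% | 77.1% / 87.3% |
| 26% vs 10% | 4.3% / 4.9% | 48.8% / 58.6% |
| 26% vs 26% (null) | 5.9% / 5.5% | 5.4% / 5.2% |

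Each pair is for affected SD 6 / 8.

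A second set-up (mean 28, between-woman SD 2, within-woman SD 2 rising to 6-10, 365 days, 600 runs) also tested the number of cycles. With 0-10% affected on placebo, mean length and frequency both rejected in about 4-6% of runs. A Mann-Whitney test on within-woman SD rejected in 54-59% (placebo 5%) and 34-35% (placebo 10%). Under similar inputs the log-SD test gave 89-95% and 61-67%, so the choice of test matters.

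**Case 2: periods are skipped or split.** Here the mean does move. If 15% of an affected woman's cycles double, her mean rises by 0.15 × 29 = 4.35 days, and the arm difference at 26% vs 5% is 0.21 × 4.35 = 0.91 days. In simulations of that case the mean-length test rejected in 43-63% of trials and the log-SD test in 85-89%. With 20-50% of affected women's cycles skipped or split, the mean-length test rejected in about 50-91% (placebo 5%) and 30-68% (placebo 10%). The log-SD test, at 55-93%, was usually but not always higher.

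**Adverse events at any grade.** Power of Fisher's exact test with 26% on SDG:

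| Placebo rate | 161 vs 81 randomised | 99 vs 49 not on OCs |
|---|---|---|
| 5% | 99% | 92% |
| 10% | 85% | 62% |
| 15% | 46% | 29% |

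A simple any-grade comparison would thus be informative if the placebo rate is well below the pilot rate.

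**The case against.** A reader might infer more than the documents support. Four stronger readings fail.

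- *Frequency and length stay unchanged when cycles become erratic.* This is true only when the mean is preserved, and Case 1 builds that in. Case 2 shows that missed or extra bleeds move both quantities.
- *The trial would report no impact.* Section 11.2 does not say that length is reduced to one mean per woman. It says only that secondary endpoints use methods similar to the primary one, a two-sample comparison of change. A mean is the natural reading but not the only one, so the supported wording is that the analysis could miss the harm.
- *Irregular menses is judged only by length or frequency.* Objective 3 includes cyclicity, section 11.2 separately lists the menstrual cycle, and adverse events are reviewed at months 1, 3, 6, 9 and 12 and graded. The harm will be recorded. What is missing is a defined comparison by arm. Discontinuation because of irregular menses would also count in the Fisher comparison.
- *The daily diary has no planned use.* It is the source for cycle length.

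The sizes are also fragile. The 26% is uncontrolled and counts any report, so it does not mean that a quarter of women cycle erratically all year. The 99 and 49 are upper limits: women not on oral contraceptives include some whose other contraception modulates the cycle, and some who do not menstruate because of an IUD, ablation or hysterectomy. Section 4.2.4 admits women with as few as four periods a year, so some will be irregular at entry and 12 cycles each is optimistic. Finally, this is one secondary outcome in a phase IIB trial and cannot alter the Ki-67 conclusion.

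All of this stands. It narrows the point and limits its weight, but supplies no planned analysis of regularity.

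**Conclusion.** The point holds in a limited form. The plan names irregular menses as a main expected adverse event and cyclicity as an objective, but it defines no measure of regularity and no test by arm for irregular menses at grade 1 or 2. A null result on average length or frequency is therefore weak evidence of no menstrual impact. Where short and long cycles cancel, a mean-length test has about 5% power. Where periods are skipped, it has partial power, usually below that of a variability measure.

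Every power figure for menstrual outcomes rests on assumed cycle inputs and an unknown placebo rate, and none should be read as a prediction. The gap lies in the analysis text, not in data collection, and it is worth closing before unblinding. The moderate-or-worse description and the grade 3 cut-off in section 11.2 also need to be reconciled with the labels in section 8.2.3.

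**What to change.** Amend section 11.2, and align Appendix 1 item 8.3 with it:

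1. In menstruating women not on cycle-modulating contraceptives, compare by randomised arm the log of the within-woman SD of on-study cycle length (unequal-variance t-test, or a regression on arm when adjusting). Adjust for pre-study regularity where the pre-study diary or history allows. Report the SDG-placebo difference with a 95% CI, and state the minimum number of cycles a woman needs to contribute.
2. Compare by arm the number of bleeding or spotting days outside the menses per woman, with outside the menses defined in advance.
3. Report irregular-menses adverse events of any grade by arm, with the risk difference, 95% CI and Fisher's exact test. Reconcile the moderate-or-worse description with the grade 3 cut-off.
4. State that any conclusion of no menstrual impact rests on regularity as well as length.

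The cost is a few lines of text and some derived variables. No new data or visits are needed, and no dosing or suspension rule changes. The downside is a few extra secondary comparisons at a 5% level that the plan already leaves uncontrolled. Adjustment in item 1 will be imperfect, because the pre-study diary may cover only a few cycles.

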Random breast FNA performed during follicular phase (Day 1-10) of menstrual cycle or if non-menstruating additional serum aliquot frozen for confirmation of follicular phase.

Serum and plasma specimens frozen for later assays in central laboratories.

CBC and **fasting** metabolic chemistry profile may be performed if desired and study entry anticipated within 3 months of RPFNA

History and physical exam may be performed if desired and study entry anticipated within 3 months of RPFNA

Subject given materials for menstrual diary recording

↓

Tissue Qualifiers for trial participation

Epithelial hyperplasia +/- atypia; Masood score ≥ 13 ; plus Ki-67 $\geq 2\%$

↓

Study Entry Visit (within six months of RPFNA)

History and physical exam (if not performed within 3 months)

Complete BCPT symptom checklist, BPQ Breast Pain Questionnaire and Lignan Diet Questionnaire. Collect Pre-study Menstrual Diary Information

CBC and **fasting** metabolic chemistry profile (if not performed within previous 3 months)

Fasting serum and plasma specimens frozen for later assays in central laboratories.

Spot (+ optional overnight) urine collection and buccal sample for later assays in central laboratories.

Negative urine pregnancy test

Randomization number assigned (next in sequence)

Study Agent dispensed – 6 month supply

Phone contacts at 1 and 3 months to monitor adverse events and concomitant meds

6-month Visit

Review of adverse events and concomitant meds

Return study agent for compliance check; New supply of study agent issued

Phone contact at 9 months to monitor adverse events and concomitant meds

2-4 Weeks Prior to Anticipated Off Study Visit (for non-menstruating women only)

Assess serum hormone levels (Estradiol, Progesterone, FSH); use for prediction of menstrual cycle and scheduling of RPFNA during follicular phase.

12-month Visit (Off-Study)

No antibiotics for the 3 weeks prior to RPFNA.

Fasting blood drawn, preferably within 3-4 hours of last dose of study agent
CBC and metabolic chemistry profile

Serum and plasma specimens frozen for later assays at central laboratories.

Spot (+ optional overnight) urine collection frozen for assay in central laboratories.

Complete BCPT symptom checklist, BPQ Breast Pain Questionnaire, Lignan Diet Questionnaire,
Collect menstrual Diary Information.

Return Study Agent.

RPFNA (Day 1-10 of menstrual cycle); for non-menstruating women, additional serum aliquots
frozen for confirmation of follicular phase.

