2.4.3 Eligibility criteria for SDG pilot study

Eligibility criteria included regular menstrual cycles, no oral contraceptives, a 3-fold or greater increase in 5-year estimated risk for breast cancer relative to SEER statistics for age group, and normal mammogram performed in the follicular phase of the menstrual cycle within 3 months of baseline RPFNA. Subjects on oral contraceptives were excluded in order to reduce subject hormonal heterogeneity and because it might be more difficult to demonstrate biomarker modulation from SDG in the face of exogenous hormones. Baseline RPFNA was also to be performed in the follicular phase and had to show unequivocal hyperplasia +/- atypia as well as a minimum Ki-67 expression of 2% in hyperplastic ducts. The Ki-67 value of 2% was chosen since this is the median Ki-67 value in hyperplastic tissue obtained by RPFNA from high risk pre-menopausal women in the follicular phase of the cycle [86]. Further, a Mayo Clinic series suggests that women having a biopsy showing atypical hyperplasia and a Ki-67 of 2% or higher have a significantly higher 10-year risk of breast cancer (14% versus 3%) [88]. The early-mid follicular phase is utilized due to greater subject comfort and less bleeding during RPFNA.

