4.4 Inclusion Criteria for Study Entry

- 4.4.1 RPFNA performed within 6 months of the Study Entry Visit and in the follicular portion (day 1-10) of the menstrual cycle. Note that day 1 is defined as the first day of bleeding. For non-menstruating women, RPFNA during the follicular phase must be confirmed by hormone levels drawn on the day of RPFNA. Either clinical laboratory results are sent to Protocol Chair for assessment of menstrual cycle phase; or an additional frozen serum aliquot is sent to KUMC for assay of hormone levels and phase confirmation. Confirmation of follicular phase will be included in the eligibility report for the potential subject.
- 4.4.2 RPFNA specimen exhibits hyperplasia +/- atypia; Masood score of ≥ 13 with ≥ 500 cells on the cytology slide.
- 4.4.3 Ki-67 $\geq 2\%$ positivity (≥ 500 cells).
- 4.4.4 Willing to continue on the same or similar type of contraception during the 12 month course of study. If using non-hormonal contraception, continue that and if hormonal contraception continue that. If heterosexually active, must be agreeable to use some form of contraception during the trial unless husband or partner has had a vasectomy or subject has had uterus removed. Safety of SDG during pregnancy has not been documented.
- 4.4.5 Have reasonable organ function as documented by CBC and metabolic chemistry profile (within 3 months prior to Study Entry Visit).
- 4.4.6 Willing to undergo a history and physical at baseline and 12 months and be contacted periodically by the trial coordinator during the 12 month study period.
- 4.4.7 Willing to repeat RPFNA at 12 months following initiation of study agent.
- 4.4.8 Willing to have blood drawn at baseline and 12 months. If non-menstruating, an additional draw will be performed at approximately 11 months so as to predict when to perform the RPFNA
- 4.4.9 Able to understand and willing to provide informed consent for the RPFNA's and study participation.

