6.0 CLINICAL EVALUATIONS AND PROCEDURES

6.1 Schedule of Events

Evaluations Procedures	Eligibility/ Pre-study visit	On Study Visit	Phone Contacts Months 1,3,9	6 Month Visit	11 Month Visit	12 Month Visit	2 Week Follow up Phone Contact
Informed Consent	X	X					
Height/Weight, Vital Signs	X	X				X	
Breast Exam	X ^c	X ^c				X	
Serum hormone assay only if non-menstruating	X ^d				X ^d		
RPFNA (day 1-10 of menstrual cycle)	X ^a					X ^a	
Serum/Plasma collection for hormone + lignan assays	X ^b					X ^b	
Screening eligibility checklist	X						
CBC + Fasting blood for chem. Profile, lignan and cytokine c-peptide		X ^{bc}				X ^b	
Urine collection (spot required, additional overnight preferred, materials to subject for menstrual diary)		X ^b				X ^b	
Medical History		X ^c					
Physical Exam		X ^c				X	
Urine Pregnancy Test		X					
Buccal sample		X ^b					
BCPT Symptom Checklist, BPQ Breast pain and lignan intake questionnaires		X				X	
Concomitant Meds.		X	X	X		X	X
Dispense Study Agent		X		X			
Adverse Events			X	X		X	X
Return Study Agent/Evaluate Compliance				X		X	
Off Study Evaluation							X

^a See specimen management section 7.0 for details on shipping of RPFNA materials to KUMC

^b To be shipped to KUMC for central analysis. See specimen management section 7.0. Notify KUMC by fax and email prior to shipment.

^c Physical, Breast exam, Baseline CBC, Medical history and fasting chem profile may be performed at RPFNA or Study Entry Visit as long as within 3 months prior to study entry.

^d If non-menstruating, blood assayed for hormone levels 2-4 weeks prior to anticipated RPFNA so as to predict timing of follicular phase.

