6.5 Evaluation at Off-Study 12 Month Visit (see section 6.1 for Study Calendar)

If necessary for synchronizing the scheduling of RPFNA with the menstrual cycle, study agent may be continued for up to two additional months, until the RPFNA is performed. If this occurs, then studies associated with the repeat RPFNA and completion of study will be conducted at that time, not at a calendar 12 months. Systemic use of antibiotics must be stopped 3 weeks prior to the off-study RPFNA procedure and for 3 weeks prior to collecting blood or urine specimens for the off-study assessment of lignan levels. The procedures may be delayed by up to two months if necessary to facilitate this.

For non-menstruating women (see section 4.2.4), hormone levels (estradiol, progesterone, and FSH) must be assayed 2-4 weeks prior to RPFNA in order to predict when to perform RPFNA so as to be in the follicular phase. Lab results and institutional normal ranges must be reviewed by the Protocol Chair, who will provide an acceptable time window within which to conduct the RPFNA.

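### Breast pain is scored on an uncontrolled cycle day at baseline but in the follicular phase at 12 months, with no alignment or adjustment, so within-arm change cannot be interpreted and the SDG-placebo comparison may lose sensitivity

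*Combined protocol and SAP*

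**What the plan says.** Section 1.0 hypothesises "a reduction in breast pain in those women entering the study with mastalgia". Section 2.2 names cyclic breast pain as the main medicinal use of lignans in young women.

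**Baseline form.** The row "BCPT Symptom Checklist, BPQ Breast pain and lignan intake questionnaires" in section 6.1 is marked only for the On Study Visit and the 12 Month Visit. The only timing rule for the On Study Visit is its distance from the screening aspiration: "RPFNA performed within 6 months of the Study Entry Visit" in section 4.4.1, and "Study Entry Visit (within six months of RPFNA" in the Schema. The Schema lists the form at that visit: "Complete BCPT symptom checklist, BPQ Breast Pain Questionnaire and Lignan Diet Questionnaire". No cycle day is required.

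**12-month form.** The off-study visit is timed to the repeat RPFNA, on day 1-10 in menstruating women and in a hormone-predicted follicular phase in non-menstruating women. If the RPFNA has to move, section 6.5 says that "studies associated with the repeat RPFNA and completion of study will be conducted at that time, not at a calendar 12 months".

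**Analysis.** Section 11.2 says "Change from baseline to 12 months will be assessed for mastalgia (expected in 30-50% of subjects at baseline", and relates that change to SDG intake, plasma lignans and urinary lignans. The between-arm methods for secondary endpoints give serum hormones and clinical laboratory tests as the markers; the BPQ is not named. Appendix 1, item 8.1 gives the BCPT checklist a four-week recall. Item 8.2 gives none for the BPQ.

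**The concern.** A symptom that may vary over the cycle is scored at any phase the first time and at one fixed phase the second time. If pain is higher in the luteal phase, many women move from a higher-pain phase to a lower-pain phase between the two forms, whichever arm they are in. A fall then appears without any drug effect. Selecting women by their baseline score adds regression to the mean in the same direction.

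The hypothesis is worded as a reduction and no between-arm BPQ test is named, so a within-arm fall could be read as support for SDG. Even the comparison between arms may suffer. Phase differences at baseline add variance to the change score, and if SDG relieves pain in proportion to its level, a follicular follow-up leaves less pain to relieve.

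Elsewhere the plan does attend to cycle phase: both RPFNAs are phase-controlled, and section 11.2 favours AMH partly because it is stable across the cycle.

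**Working it through.** **Plan's own figure.** The plan gives no power, SD or effect size for the BPQ. The nearest figure is the 83% power for Ki-67 in section 11.1 (220 evaluable, 2:1, difference 2.5, SD 6, two-sided 5%). SE = 6 × √(1/146.7 + 1/73.3) = 0.858; 2.5/0.858 = 2.91; power = Φ(2.91 − 1.96) = 0.83. It reproduces, but says nothing about the BPQ.

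**Women affected.**
- Mastalgia cases: 0.30 × 220 = 66 to 0.50 × 220 = 110.
- Section 11.1 expects 72 oral contraceptive (OC) users and 148 non-users. Cases among non-users, if prevalence is the same: 0.30 × 148 = 44.4 to 0.50 × 148 = 74.
- Assuming a 28-day cycle and entry visits spread evenly over it, 18/28 = 0.643 of entry visits fall outside day 1-10.
- Phase-mismatched cases among non-users: 0.643 × 44.4 ≈ 29 to 0.643 × 74 ≈ 48.

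**Additive phase effect (illustration).** Assume an SD of change of 1 without a phase effect, a luteal excess *c*, half of baseline forms luteal, all 12-month forms follicular, and an SDG effect of 0.5 SD. Placebo change is −*c*/2, that is −0.25, −0.50 and −0.75 SD for *c* = 0.5, 1.0 and 1.5. The arm difference stays at −0.50 and type I error at about 5%. Simulated power:

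| Cases | *c* = 0 | 0.5 | 1.0 | 1.5 |
|---|---|---|---|---|
| 66 | 47% | 45% | 39% | 32% |
| 110 | 69% | 66% | 60% | 50% |

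The loss runs from 47 − 45 = 2 to 69 − 50 = 19 points.

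**Proportional effect (illustration).** Assume 220 women randomised 2:1, luteal pain gamma (shape 1, scale 2), error SD 1, mastalgia defined as baseline score ≥ 2, a 30% proportional SDG effect and a t-test on change. Power:

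| Follicular pain as share of luteal | As scheduled | As scheduled, no phase effect in 72 OC users | Both follicular | Both luteal |
|---|---|---|---|---|
| 50% | 27% | 49% | 37% | about 94% |
| 70% | 59% | 70% | 69% | about 94% |
| 90% | 88% | 90% | 90% | about 94% |

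Repeat runs moved single figures by up to about 4 points. Placebo scores fall by about 51%, 33% and 19% as scheduled, against about 12% with both forms luteal. With no SDG effect, type I error stays near 5%.

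**Splitting the loss.** Mismatch alone: 37 − 27 = 10, 69 − 59 = 10 and 90 − 88 = 2 points. Scoring in the follicular phase at all: 94 − 37 = 57, 94 − 69 = 25 and 94 − 90 = 4 points.

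**Effect of adjustment.** Under the same model, adjusting for baseline score gave the scheduled design about 49%, 74% and 89%. Adding phase as a covariate gained only about 0 to 3 points more.

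**The case against.** The strongest objection is that the mechanism depends on a form whose recall period the documents do not give. With four-week recall, as on the BCPT checklist, visit day would matter little. Even a one- or two-week recall on day 1-10 would often reach back into the previous luteal phase. This stands as a condition on the whole point.

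Second, section 4.5.8 places the baseline questionnaires before randomisation, and both arms follow the same schedule, so a common additive shift cancels. This also stands: the arm difference is not biased by such a shift, and the type I error holds.

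Third, no natural-cycle effect can be assumed in OC users, or in women with an IUD, ablation or hysterectomy. That reduces the loss, as the table shows, but does not remove it.

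Fourth, the both-luteal benchmark is in effect a different endpoint. That is fair, and is why the loss is split above.

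A reader might cite section 2.4.3, "The early-mid follicular phase is utilized due to greater subject comfort and less bleeding during RPFNA", as the plan's own statement that mastalgia is lower in that phase. It is not: the sentence concerns comfort during the needle procedure, in the pilot section. Nothing in the documents says that pain scores are lower then.

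**Conclusion.** The asymmetry in timing is documented, and neither alignment nor adjustment is planned. If BPQ recall is shorter than a cycle and pain is partly cyclic, within-arm change in mastalgia cannot be interpreted. The randomised comparison remains valid but may be less sensitive. Its loss ranges from a few points to most of the power, depending wholly on assumptions about scores, phase effect and drug effect that the documents do not supply.

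Two stronger readings are not supported. One is that a real SDG effect will be hidden. That comes close to true only if SDG acts mainly on luteal pain and follicular scores are near zero. For example, with a 40% proportional effect, luteal mean 3, follicular mean 0.5, SD 1 and a floor at 0, power is about 7%, against 89% to 98% with both forms luteal. The other is that soreness from the screening aspiration inflates the baseline score. The documents report no lasting pain, entry waits for the tissue result, and any such effect would be balanced by arm.

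This is one quality-of-life component among the secondary objectives. The point is a cheap improvement, not a threat to the trial's main conclusion.

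**What to change.** 1. State the BPQ recall period. If it covers a full cycle, items 2 and 3 matter little.
2. For menstruating women not yet assessed, have the BPQ completed and dated at home with the menstrual diary, in the same pre-specified cycle window at both time points (for example the week before expected menses) and before any aspiration. At baseline this means issuing the materials ahead of the screening RPFNA. If that is not practical, use a window between screening and randomisation.
3. For all women, specify mastalgia change as an SDG-placebo comparison adjusted for baseline BPQ score, with diary-derived cycle day at each BPQ as a covariate. The baseline score brings most of the gain from adjustment.
4. State that no conclusion will be drawn from within-arm change.

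This needs short amendments to sections 6.1, 6.3.6, 6.5.4 and 11.2. The form is self-completed and the diary already runs from before entry to the off-study visit, so no visit is added. The costs are some late forms, imprecise timing in women with irregular cycles (section 4.2.4 requires only four periods a year), and two timing regimes in one trial. Women already enrolled can be handled only by adjustment.
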